### 10.3.2 Distribution of Adverse Event Reports

CTEP-AERS is programmed for automatic electronic distribution of reports to the following individuals: Principal Investigator and Adverse Event Coordinator(s) (if applicable) of the Corresponding Organization or Lead Organization, the local treating physician, and the Reporter and Submitter. CTEP-AERS provides a copy feature for other e-mail recipients.

### 10.3.3 Expedited Reporting Guidelines

Use the NCI protocol number and the protocol-specific patient ID assigned during trial registration on all reports.

**Note: A death on study requires both routine and expedited reporting, regardless of causality. Attribution to treatment or other cause must be provided.**

Death due to progressive disease should be reported as **Grade 5 “Disease progression”** in the system organ class (SOC) “General disorders and administration site conditions.” Evidence that the death was a manifestation of underlying disease (*e.g.*, radiological changes suggesting tumor growth or progression: clinical deterioration associated with a disease process) should be submitted.

### Phase 1 and Early Phase 2 Studies: Expedited Reporting Requirements for Adverse Events that Occur on Studies under an IND/IDE within 30 Days of the Last Administration of the Investigational Agent/Intervention 

FDA REPORTING REQUIREMENTS FOR SERIOUS ADVERSE EVENTS (21 CFR Part 312)  NOTE: Investigators MUST immediately report to the sponsor (NCI) ANY Serious AEs, whether or not they are considered related to the investigational agent(s)/intervention (21 CFR 312.64)                  An AE is considered serious if it results in ANY of the following outcomes:
 
 
1) Death
 
2) A life-threatening AE
 
3) An AE that results in inpatient hospitalization or prolongation of existing hospitalization for ≥ 24 hours
 
4) A persistent or significant incapacity or substantial disruption of the ability to conduct normal life functions
 
5) A congenital anomaly/birth defect.
 
6) Important Medical Events (IME) that may not result in death, be life threatening, or require hospitalization may be considered serious when, based upon medical judgment, they may jeopardize the patient or subject and may require medical or surgical intervention to prevent one of the outcomes listed in this definition. (FDA, 21 CFR 312.32; ICH E2A and ICH E6).
 
		

ALL SERIOUS AEs that meet the above criteria MUST be immediately reported to the NCI via electronic submission within the timeframes detailed in the table below.
		
Hospitalization	Grade 1 and Grade 2 Timeframes	Grade 3-5 Timeframes
Resulting in Hospitalization ≥ 24 hrs	10 Calendar Days	24-Hour 5 Calendar Days
Not resulting in Hospitalization ≥ 24 hrs	Not required	

NOTE: Protocol specific exceptions to expedited reporting of serious AEs are found in the Specific Protocol Exceptions to Expedited Reporting (SPEER) portion of the CAEPR.
 
Expedited AE reporting timelines are defined as:
 
 
○ “24-Hour; 5 Calendar Days” - The AE must initially be submitted electronically within 24 hours of learning of the AE, followed by a complete expedited report within 5 calendar days of the initial 24-hour report.
 
○ “10 Calendar Days” - A complete expedited report on the AE must be submitted electronically within 10 calendar days of learning of the AE.
 
		

Serious AEs that occur more than 30 days after the last administration of investigational agent/intervention and have an attribution of possible, probable, or definite require reporting as follows:
		

**Expedited 24-hour notification followed by complete report within 5 calendar days for:**

- All Grade 3, 4, and Grade 5 AEs

**Expedited 10 calendar day reports for:**

- Grade 2 AEs resulting in hospitalization or prolongation of hospitalization

For studies using PET or SPECT IND agents, the AE reporting period is limited to 10 radioactive half-lives, rounded UP to the nearest whole day, after the agent/intervention was last administered. Footnote “1” above applies after this reporting period.

Effective Date: May 5, 2011

#### 10.3.4 Olaparib Adverse Events of Special Interest

AEs of special interest (AESI) are events of scientific and medical interest specific to the further understanding of olaparib’s safety profile and require close monitoring and rapid communication by the investigators to CTEP. An AESI may be serious or non-serious. The AESI for olaparib are the following Important Potential Risks:

1. MDS/AML
2. New primary malignancy (other than MDS/AML)
3. Pneumonitis
4. Cases of potential drug-induced liver injury (DILI) that include an elevated ALT or AST in combination with either an elevated bilirubin or clinical jaundice, as defined by Hy’s Law and based on the following observations:
  - Treatment-emergent ALT or AST  $>3\times$ ULN (or  $>3\times$  baseline value in disease states where LFTs may be elevated at baseline) in combination with total bilirubin  $>2\times$ ULN (of which  $\geq 35\%$  is direct bilirubin).
  - Treatment-emergent ALT or AST  $>3\times$ ULN (or  $>3\times$  baseline value in disease states where LFTs may be elevated at baseline) in combination with clinical jaundice.

**Any** event of MDS/AML, new primary malignancy, pneumonitis, or potential DILI should be reported in an expedited manner to CTEP via Medidata Rave regardless of whether it is considered a non-serious AE (*e.g.*, non-melanoma skin cancer) or SAE, and regardless of the investigator’s assessment of causality or knowledge of the treatment arm. For cases of potential DILI, report all relevant laboratory abnormalities and related AEs using the appropriate CTCAE terms.

Events of MDS, AML, or new primary malignancy occurring more than 30 days after the last study treatment must be reported via Medidata Rave regardless of seriousness or causality. Investigators will be asked during the regular follow-up for OS if the patient has developed MDS/AML or a new primary malignancy and prompted to report any such cases.

#### 10.3.5 Additional Protocol-Specific Expedited Adverse Event Reporting Exclusions

For this protocol only, the AEs/grades listed below do not require expedited reporting via Medidata Rave. However, they still must be reported through the routine reporting mechanism (Section 10.4):

CTCAE SOC	Adverse Event	Grade	≥24h Hospitalization a
Investigations	Neutrophil Count Decreased	4	Regardless
Investigations	Platelet Count Decreased	4	Regardless
Blood & Lymphatic System Disorders	Anemia	4	Regardless

a Indicates that an AE required hospitalization for ≥24 hours or prolongation of hospitalization by ≥24 hours of a patient.

#### 10.4 Routine Adverse Event Reporting

All AEs **must** be reported in routine study data submissions. **AEs reported expeditiously through Medidata Rave must also be reported in routine study data submissions.**

AE data collection and reporting, which are required as part of every clinical trial, are done to ensure the safety of patients enrolled in the studies as well as those who will enroll in future studies using similar agents. AEs are reported in a routine manner at scheduled times during the trial using Medidata Rave. For this trial the AE CRF is used for routine AE reporting in Rave.

#### 10.5 Pregnancy

Although not an AE in and of itself, pregnancy as well as its outcome must be documented via **Medidata Rave**. In addition, the ***Pregnancy Information Form*** included within the NCI Guidelines for Adverse Event Reporting Requirements must be completed and submitted to CTEP. Any pregnancy occurring in a patient or patient’s partner from the time of consent to 90 days after the last dose of study drug must be reported and then followed for outcome. Newborn infants should be followed until 30 days old. Please see the “NCI Guidelines for Investigators: Adverse Event Reporting Requirements for DCTD (CTEP and CIP) and DCP INDs and IDEs” (at [http://ctep.cancer.gov/protocolDevelopment/adverse\\_effects.htm](http://ctep.cancer.gov/protocolDevelopment/adverse_effects.htm)) for more details on how to report pregnancy and its outcome to CTEP.

#### 10.6 Secondary Malignancy

A *secondary malignancy* is a cancer caused by treatment for a previous malignancy (e.g., treatment with investigational agent/intervention, radiation or chemotherapy). A secondary malignancy is not considered a metastasis of the initial neoplasm.

CTEP requires all secondary malignancies that occur following treatment with an agent under an NCI IND/IDE be reported expeditiously via Medidata Rave. Three options are available to describe the event:

- Leukemia secondary to oncology chemotherapy (e.g., AML)
- MDS
- Treatment-related secondary malignancy

*NCI Protocol #:* 10264

*Version Date:* December 11, 2024

Any malignancy possibly related to cancer treatment (including AML/MDS) should also be reported via the routine reporting mechanisms outlined in each protocol.

### **10.7 Second Malignancy**

A second malignancy is one unrelated to the treatment of a prior malignancy (and is **NOT** a metastasis from the initial malignancy). Second malignancies require **ONLY** routine AE reporting unless otherwise specified.

## 11. STUDY CALENDAR

Baseline evaluations are to be conducted within 1 week prior to start of protocol therapy. Scans and x-rays must be done  $\leq 4$  weeks prior to the start of therapy. In the event that the patient's condition is deteriorating, laboratory evaluations should be repeated within 48 hours prior to initiation of the next cycle of therapy.

	Pre-Study	Cycle 1 +/-1	Cycle 2 +/-1	Cycle 3 +/-1	Cycle 4 +/-3	Cycle 5 +/-3	Cycle 6 +/-3	Cycle 7 +/-3	Cycle 8 +/-3	Cycle 9 +/-3	Cycle 10 +/-3	Cycle 11 +/-3	Cycle 12+ +/-3	EOT +/-7	90 day f/u a +/-14
Olaparib		A	A	A	A	A	A	A	A	A	A	A	A		
Informed consent	X														
Demographics	X														
Medical history	X														
Concurrent meds	X	X.....X													
Physical exam b	X	X	X	X	X	X	X	X	X	X	X	X	X	X	X
Vital signs	X													X	X
Height	X														
Weight	X	X	X	X	X	X	X	X	X	X	X	X	X		X
Performance status b	X	X	X	X	X	X	X	X	X	X	X	X	X		X
CBC w/diff, plts f	X	X	X	X	X	X	X	X	X	X	X	X	X		X
Coagulation evaluation g	X	X	X		X		X			X			X	X	
Serum chemistry c, f	X	X	X	X	X	X	X	X	X	X	X	X	X		X
Urine testing f	X	X	X		X		X		X		X		X	X	
EKG (as indicated)	X														
Adverse event evaluation		X.....X												X	
Pregnancy test d	X														
Response assessment e without prior IDH inhibitor exposure		X		X			X			X			X		
Response assessment e with prior IDH inhibitor exposure				X			X			X			X		
Bone marrow aspiration	X	X		X			X			X			X	X	
Blood collection for biomarker assays h	X	X		X			X			X			X	X	
Buccal swab	X														

*NCI Protocol #: 10264*

*Version Date: December 11, 2024*

- A: Olaparib: Dose as assigned; 200 or 300 mg q12h daily PO.
- a: 90 day f/u evaluation.
- b: Note: Physical exams and Performance status evaluations are based on a 4-week cycle. At minimum, performance status should be evaluated at the beginning of every cycle.
- c: CBC with differential and platelets assessment to occur twice weekly during Week 1 of Cycle 1, once weekly during Weeks 2-4 of Cycle 1, and then once per cycle thereafter. Assessment to include albumin, alkaline phosphatase, total bilirubin, bicarbonate, BUN, calcium, chloride, creatinine, glucose, LDH, phosphorus, potassium, total protein, SGOT [AST], SGPT [ALT], sodium, uric acid.
- d: Pregnancy test for women of childbearing potential.
- e: Response Assessment includes bones marrow biopsy, and marrow and plasma 2HG levels. Response per AML IWG (IWG) 2003 criteria and MDS IWG 2006 (modification) criteria.

- f: Clinical Safety Laboratory Assessments to occur twice weekly during Week 1 of Cycle 1, once weekly during Weeks 2-4 of Cycle 1, and then once per cycle. Assessment to include: Haematology/Haemostasis (whole blood), B-Haemoglobin (Hb), B-Leukocyte count, B-Absolute neutrophil count, B-Absolute lymphocyte count, B-Platelet count, B-Mean cell volume (MCV), Urinalysis (dipstick), U-Hb/Erythrocytes/Blood, U-Protein, U-Glucose, and Clinical Chemistry (serum or plasma): S/P-Creatinine, S/P-Bilirubin, total, S/P- Alkaline phosphatase (ALP), S/P-Aspartate transaminase (AST), S/P-Alanine transaminase (ALT), S/P-Albumin, S/P-Potassium, S/P-Calcium, total, S/P-Sodium, S/P-Urea or Blood Urea Nitrogen (BUN), S/P-Total Protein, S/P lactate dehydrogenases (LDH), S/P uric acid, & phosphorus
- g Coagulation evaluation to occur twice weekly during Week 1 of Cycle 1, once weekly during Weeks 2-4 of Cycle 1, and then once per cycle thereafter. Assessment to include activated partial thromboplastin time (APTT), Prothrombin Time/international normalized ratio (PT/INR), and Fibrinogen as indicated in the calendar, or as clinically indicated (*i.e.*, upon suspicion of DIC). Each coagulation test result will be recorded in CRF. Coagulation evaluation to be conducted pre-study, Cycle 1 Day 1, Cycle 1 Day 15, and Day 1 of Cycles 2, 4, 6, 9, 12, every third cycle after cycle 12, and at End of Treatment.
- H Blood and bone marrow collections to occur after the cycle.
- Note: Each Cycle is 28 days.; Visit Windows: Cycle 1 – 3 (+/-1 day); Cycle 4 – 12+ (+/-3 days); EOT +/- 7 days; 90 f/u +/-14 days

EOT= end of treatment, q12h = every 12 hours, PO = by mouth, BUN=blood urea nitrogen; LDH=lactic dehydrogenase; SGOT[AST]=serum glutamic oxaloacetic transaminase [aspartate transaminase]; SGPT[ALT]=serum glutamic pyruvic transaminase [alanine transaminase]. CRF = Case Report Form.

## 12. MEASUREMENT OF EFFECT

### 12.1 Antitumor Effect – Hematologic Tumors

For patients not previously exposed to IDH inhibitors, response is assessed after cycles 1, 3, 6, 9, and 12 for the first year. For patients *with* prior IDH inhibitor exposure, response is assessed after cycles 3, 6, 9, and 12 for the first year on treatment.

Category	Definition	Comment
Complete Response (CR)	Bone marrow blasts <5%; absence of circulating blasts and blasts with Auer rods; absence of extramedullary disease; ANC $\geq 1.0 \times 10^9/L$ (1,000/mcL); platelet count $\geq 100 \times 10^9/L$ (100,000/mcL)*	
CR with incomplete hematologic recovery (CRi)/CRh	All CR criteria except for residual neutropenia ( $<1.0 \times 10^9/L$ [1,000/mcL]) or thrombocytopenia ( $<100 \times 10^9/L$ [100,000/mcL])* CRh: complete remission with partial hematological recovery (platelets > 50,000 mcL and ANC > 500/mcL)	
Morphologic leukemia-free state (“marrow CR”, MLFS)	Bone marrow blasts <5%; absence of blasts with Auer rods; absence of extramedullary disease; no hematologic recovery required	Marrow should not merely be aplastic—at least 200 cells should be enumerated, or cellularity should be at least 10%
Partial response (PR)	All hematologic criteria of CR; decrease of bone marrow blast percentage to between 5% and 25%; and decrease of pretreatment bone marrow blast percentage by at least 50%	Especially important in the context of phase 1-2 clinical trials
Stable disease (SD)	Absence of CR, CRi, PR, MLFS; and criteria for PD not met	The period of stable disease should last at least 3 months

Category	Definition	Comment
Progressive disease (PD)	Evidence for an increase in bone marrow blast percentage and/or increase of absolute blast counts in the blood: 
 
• >50% increase in marrow blasts over baseline (a minimum 15% point increase is required in cases with <30% blasts at baseline; or persistent marrow blast percentage of >70% over at least 3 months; without at least a 100% improvement in ANC to an absolute level (<math>>0.5 \times 10^9/L</math> [500/mcL], and/or platelet count to <math>>50 \times 10^9/L</math> [50,000/mcL] nontransfused)
 
• >50% increase in peripheral blasts (WBC <math>\times</math> % blasts) to <math>>25 \times 10^9/L</math> (<math>>25,000/mcL</math>) (in the absence of differentiation syndrome**)
 
• New extramedullary disease
 
	In general, at least two cycles should be administered prior to PD assessment.  Patients with PD may remain on study, after discussion with the PI, if it is judged that they are deriving clinical benefit from doing so.
Primary refractory disease	No CR or CRi after two courses of intensive induction treatment; excluding patients with death in aplasia or death due to indeterminate cause	
Death in aplasia	Death occurring $\geq 7$ days following completion of initial treatment while cytopenic; with aplastic or hypoplastic bone marrow obtained within 7 days of death, without evidence of persistence leukemia	
Death due to indeterminate cause	Deaths occurring before completion of therapy, or $< 7$ days following its completion; or deaths occurring $\geq 7$ days following completion of initial therapy with no blasts in the blood, but no bone marrow examination available	
Hematologic relapse (after CR, CRi)	Bone marrow blasts $\geq 5\%$ ; or reappearance of blasts in the blood; or development of extramedullary disease	
* CBC values for up to 14 days after bone marrow assessment may be used to determine response. ** Certain targeted therapies, e.g. , those inhibiting mutant IDH proteins, may cause a differentiation syndrome, i.e. , a transient increase in the percentage of bone marrow blasts and an absolute increase in blood blasts. In the setting of therapy with such compounds, an increase in blasts may not necessarily indicate PD. ANC=absolute neutrophil count, IDH=isocitrate dehydrogenase, MFC=multiparameter flow cytometry, RT-qPCR=real-time quantitative polymerase chain reaction, WBC=white blood count. (Döhner et al. , 2017)		

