### 2.3 Rationale

As shown in the study schema the proposed study is a 4-arm Phase 2, open-label study of PARP inhibition (olaparib) in advanced relapsed or refractory *IDH1/2*-mutant AML and MDS. At present, an IDH2 and IDH1 inhibitor, enasidenib and ivosidenib respectively, are FDA approved for the management of patients with IDH2 mutant leukemia (Stein *et al.*, 2015; DiNardo *et al.*, 2018). Based on the scientific rationale described (synthetic lethality of the mutant clone due to accumulation of toxic metabolites), we hypothesize that inhibition of mutant IDH1/2 with small molecule inhibitors is not the most efficacious approach to treat IDH mutant leukemia. Indeed, the synthetic lethality of olaparib is likely most robust in the setting of IDH mutant activity (due to oncometabolite accumulation), and possibly blunted to some degree with the use of an IDH inhibitor. Therefore, we propose a separate arm for evaluation of patients pretreated with IDH inhibitor therapy. In addition, we propose the inclusion of IDH inhibitor-naïve AML patients who present within a "window of opportunity" in this trial (IDH inhibitors are yet to be approved in the MDS setting. AML and MDS have been separated as they are distinct diagnoses, and within each disease group patients have been separated by their exposure to IDH inhibitors; IDH inhibitor naïve and IDH inhibitor exposed. Recognizing that other FDA approved therapeutic options are available, but also that these patients may have a dramatic response to olaparib monotherapy, IDH inhibitor naïve patients will be monitored very closely, including frequent bloodwork and bone marrow evaluation 4 week (or earlier as needed) to safeguard against progression and allow for transition to standard of care therapy within the 12-week period prior to response assessment in the case of progression.

Relapsed/ refractory patients may also have co-occurring targetable mutations, such as FLT3 ITD. At the present time there is no consensus in the AML community on the ideal sequencing of targeted therapies when multiple options are applicable. This is reflected in the current NCCN AML recommendations. In these situations, we will need to rely on the judgement of the local

investigator/ provider to choose the optimal therapeutic option.

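### The two-cycle wait before PD assessment in Section 12.1 makes no exception for IDH-inhibitor-naive patients and is in tension with their cycle-1 response assessment

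*Combined protocol and SAP*

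**What the plan says.** Section 2.3 accepts that naive patients have other approved options. It supports enrolling them with close monitoring, including "bone marrow evaluation 4 week (or earlier as needed) to safeguard against progression and allow for transition to standard of care therapy", within the 12 weeks before response assessment. It also notes that "IDH inhibitors are yet to be approved in the MDS setting".

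Section 12.1 carries this into the schedule. For naive patients, "response is assessed after cycles 1, 3, 6, 9, and 12 for the first year". For exposed patients, "response is assessed after cycles 3, 6, 9, and 12 for the first year on treatment". The study calendar agrees: only the response-assessment row for patients "without prior IDH inhibitor exposure" has a mark at cycle 1.

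The PD row of the 12.1 table has two comments. The first is "In general, at least two cycles should be administered prior to PD assessment", with no cohort named. The second begins "Patients with PD may remain on study, after discussion with the PI" and makes this conditional on a judgment that the patient benefits clinically.

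Section 6.3 lists the events that end treatment. Disease progression is one, with no exception. Clinical progression and investigator judgment are listed separately. For naive patients, so is the absence of CR/CRh/mCR, with no time point.

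Section 9.4.3 runs PFS and DOR to the documentation of progression, death or last follow-up. Section 9.6.2 treats a patient as evaluable for response only after at least one finished cycle.

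**The concern.** The cycle-1 assessment exists for naive patients because an approved alternative may be waiting for them. A site that follows the 12.1 comment may look at a week-4 marrow that meets the PD definition and still not record PD, at the visit meant to detect it. The move to standard care then depends on the more general exits in Section 6.3. By the protocol's own account of approvals, foregone approved therapy is mainly an issue in the naive AML arm.

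There is also a data-quality side. If some sites apply the comment and others do not, the same marrow yields different progression dates, and PFS depends on that date. DOR could be affected too, but only if a response is documented and progression then appears before two cycles are complete.

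**Working it through.** This is a check of consistency and timing; no power or error-rate formula is involved.

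**Inputs**
- Cycle length: "Each Cycle is 28 days" (study calendar notes).
- Wait before PD assessment: two cycles, in general (12.1).
- Naive assessments in the first year: after cycles 1, 3, 6, 9 and 12 (12.1).
- Exposed assessments in the first year: after cycles 3, 6, 9 and 12 (12.1).
- Protected window: 12 weeks before response assessment (2.3).

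**Step 1: reproduce the plan's own figures.** 3 × 28 = 84 days = 12 weeks, so the 12-week response assessment in 2.3 is the end-of-cycle-3 visit. 1 × 28 = 28 days = 4 weeks, so the 4-week marrow in 2.3 is the end-of-cycle-1 visit. The schedule and the rationale agree.

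**Step 2: place the wait on that timeline.** Two cycles end on day 2 × 28 = 56 (week 8). The cycle-1 assessment comes 56 − 28 = 28 days before that. No assessment is scheduled after cycle 2, so the first scheduled one that satisfies the wait is day 84.

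**Step 3: delay in a formal PD call.**

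| PD recorded at | Day | Delay from day 28 |
|---|---|---|
| End of cycle 1 (naive exempt) | 28 | 0 days |
| Unscheduled marrow once two cycles are complete | 56 | 56 − 28 = 28 days |
| Next scheduled assessment (end of cycle 3) | 84 | 84 − 28 = 56 days |

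Day 84 is also the end of the window that 2.3 meant to protect. Visit windows of ±1 day in cycles 1 to 3 are ignored.

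**Step 4: which scheduled assessments the comment touches.** Assessments before day 56 are 1 of 5 for naive patients (cycle 1) and 0 of 4 for exposed patients. The only scheduled response assessment inside the wait is therefore the one added for naive patients.

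**Step 5: other routes off treatment before day 56.**
- *Section 6.3, clinical progression and investigator judgment.* Both are available at any time; neither needs a PD label.
- *Section 6.3, absence of CR/CRh/mCR in naive patients.* A marrow that meets PD also lacks these responses, so this bullet permits an exit at week 4. It does not require one, because it is undated. Enforced at day 28, it would remove every naive patient not yet in response, which fits poorly with a primary endpoint accumulated over six cycles (9.1.2.1).
- *Section 3.2.6.* Withdrawal is mandatory if the white count exceeds 50,000/mcl more than 14 days after starting. Blood counts are twice weekly in week 1 and weekly in weeks 2 to 4.

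The case not clearly covered is progression seen on the marrow alone in a clinically stable patient.

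**Step 6: endpoints.** The Simon rules count composite CR responders (17 or more of 39 in each naive arm). A PD date does not enter that count. PFS uses the date directly: for a patient with no earlier event, the same day-28 marrow can give a PFS time of about 28 or about 84 days, depending on how the site reads the comment.

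**The case against.** The best defence is that the safeguard does not depend on the PD label. The comment is advisory: it sits in a comment column and is worded as a general recommendation. The schedule for naive patients is the more specific instruction, so a site could treat their cycle-1 visit as outside the general case. Section 2.3 can also be read as describing a safety check that comes before the formal week-12 response assessment. The exits in 6.3 and 3.2.6 remain open, and proliferative progression is covered by a hard rule and frequent blood counts.

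Most of this stands, and it limits the point. It does not remove it: 12.1 and the calendar call the cycle-1 visit a response assessment, and the text does not tell a site which instruction prevails.

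Some stronger readings are tempting, but the documents do not support them.
- *That the comment cancels the week-4 safeguard.* The wording is soft and the other exits remain. The delay is in the PD call, not necessarily in care.
- *That 12.1 and 6.3 flatly contradict each other on treatment after PD.* Section 12.1 speaks of staying on study, while 6.3 governs treatment. The reference to clinical benefit suggests continued olaparib but does not say so. This is an ambiguity.
- *That olaparib after PD should be barred by default in naive AML.* That is a clinical preference; the documents do not settle it.
- *That the wait biases the response rate through the evaluable set.* A patient with PD at the end of cycle 1 has finished a cycle and is already evaluable under 9.6.2. Loss of patients stopped earlier is a separate matter, which the wait does not cause.

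**Conclusion.** The point holds in a limited form. The two-cycle comment has no naive exception, and the only scheduled response assessment it touches is the cycle-1 visit created for naive patients. It could defer a formal, marrow-only PD call by 56 days on the schedule, or by 28 days if an unscheduled marrow is done at day 56. The consequences are a less clear trigger for considering standard care and inconsistent PD dating for PFS and, more narrowly, DOR. Composite CR and the Simon boundaries do not change.

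This rests on two assumptions: that some sites would follow the comment at the cycle-1 visit, and that some naive patients would have marrow findings meeting PD by day 28 without another reason to stop. The documents give no rate for either, so the number of patients affected cannot be estimated. The change is worth making because Section 2.3 relies on this visit to support enrolling these patients.

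**What to change.** 1. **Section 12.1, PD comment.** State that the two-cycle wait does not apply to patients without prior IDH inhibitor exposure. Findings that meet the PD definition at the end-of-cycle-1 assessment, or at an earlier as-needed marrow, are recorded as PD and prompt consideration of standard care.
2. **Sections 6.3 and 12.1.** Use one rule on whether olaparib may continue after PD. Give the absence-of-CR/CRh/mCR stop for naive patients a time point. The end of cycle 3 would match the 12-week response assessment in 2.3, but the choice belongs to the study team.
3. **Section 9.6.2, as a separate point.** State that a patient stopped for PD before completing cycle 1 counts as a non-responder. The current rule drops such patients from the denominator.

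The cost is a few sentences in three sections and no new procedures, since the cycle-1 assessment and marrow are already scheduled. The downside is that a few naive patients with an early blast rise, who might have responded later, may stop sooner.

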#### 9.4.2 Evaluation of Objective Response Rate

The effectiveness of the drug in patients for each cohort will be independently assessed by composite CR rate (CR+CRi+CRh). Objective Response Rate (ORR) will be included as a secondary endpoint, calculated as a composite CR+MLFS+PR. The exact two-sided 95% confidence intervals for the ORR will be reported. For lifetime data analyses, e.g., overall and progression free survival, the study survival will be estimated using the Kaplan-Meier method with the 95% confidence intervals (CIs). The CI based on the Greenwoods variance will be reported. In addition, the possible risk factors will be compared for survival with log-rank test. For multivariate analysis, the proportional hazards Cox model will be applied to investigate potential prognostic factors, such as age and stage of disease on the survival data. The adjusted p-values of the odds ratios and the adjusted 95% confidence interval will be reported.

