#### 9.4.3 Survival Definitions

- OS will be defined by the time interval between the first day of therapy to the time of death or last follow-up, whichever comes first.
- PFS will be defined by the time interval between the first day of therapy to the time of documentation of progression, death of any cause, or last follow-up, whichever comes first.
- DOR will be defined by the time interval between the first documentation of response to the time of documentation of progression, death of any cause, or last follow-up, whichever comes first.
- 

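### Section 12.1 gives MLFS and PR no loss-of-response criterion, so duration of response can keep running after the response is plainly lost

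*Combined protocol and SAP*

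**What the plan says.** - **What counts as a response.** Section 9.4.2 has the objective response rate "calculated as a composite CR+MLFS+PR". Objective 1.2.4 is to establish DOR.
- **What starts and ends DOR.** Section 9.4.3: "DOR will be defined by the time interval between the first documentation of response to the time of documentation of progression", with death from any cause and last follow-up as the other end points. Relapse and loss of response are not named for any type of responder.
- **Relapse.** The row in 12.1 is labelled "Hematologic relapse (after CR, CRi". It requires marrow blasts of 5% or more, "or reappearance of blasts in the blood; or development of extramedullary disease".
- **PD in 12.1.** There are two marrow limbs. The first is a rise of more than 50%, worded as "increase in marrow blasts over baseline", and "a minimum 15% point increase is required in cases with" baseline blasts below 30%. The second is marrow blasts persistently above 70% for at least 3 months without a stated improvement in neutrophils and/or platelets. Two further limbs cover peripheral blasts (more than 50% increase, to above 25 x 10^9/L) and new extramedullary disease.
- **Stable disease in 12.1** is the residual category: "Absence of CR, CRi, PR, MLFS; and criteria for PD not met". A comment adds that it should last at least 3 months.
- **MLFS and PR in 12.1.** MLFS needs marrow blasts below 5% and no count recovery. PR needs marrow blasts between 5% and 25%, at least a 50% fall from pretreatment, and the blood-count criteria of CR.

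**The concern.** A DOR estimate needs a defined start and a defined end for every kind of response it includes. MLFS and PR have a start but no end of their own. The relapse row leaves them out, and no PD limb refers to the best response reached. Followed as written, a patient can stop meeting every response criterion, fall into the residual stable-disease category at that assessment, and still contribute response time until a late PD limb is met, the patient dies, or follow-up ends.

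At stake is secondary objective 1.2.4. Late or missing end events push the DOR estimate upward, and most in patients who enter with high blast counts, because the first PD limb scales with the starting level.

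**Working it through.** The plan states no figure to reproduce here. The check applies the PD row of 12.1 to a range of baselines.

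**Meaning of baseline.** Section 12.1 does not define it. The study calendar (section 11) places baseline evaluations within 1 week before therapy, so it is taken as the pretreatment value b.

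**Marrow limb 1.** Blasts must exceed 1.5 x b. If b < 30%, the rise must also be at least 15 points. Since b + 15 is larger than 1.5b whenever b < 30, the threshold there is b + 15.

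**Marrow limb 2.** Blasts above 70% for at least 3 months without count improvement. This caps what can persist once 1.5b > 70, that is, from b = 70/1.5 = 46.7% upward.

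After an MLFS with 3% blasts, provided the peripheral-blast and extramedullary limbs are not met:

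| Baseline | Limb 1 threshold | Regrowth possible with no marrow PD |
|---|---|---|
| 10% | 10 + 15 = 25% | just under 25% |
| 20% | 20 + 15 = 35% | just under 35% |
| 40% | above 1.5 x 40 = 60% | 60% |
| 60% | above 1.5 x 60 = 90% | 70% indefinitely; up to 90% for under 3 months |

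**Size for MLFS.** The MLFS marrow criterion fails at 5%. The values above are 25/5 = 5, 35/5 = 7, 60/5 = 12 and 70/5 = 14 times that level.

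**Size for PR.** The 5% level cannot mark loss of PR, because PR itself allows 5% to 25%. PR stops being met above the smaller of 25% and 0.5b:

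| Baseline | PR blast limit | Limb 1 threshold | Ratio |
|---|---|---|---|
| 20% | 10% | 35% | 3.5 |
| 40% | 20% | 60% | 3.0 |
| 60% | 25% | 90% | 3.6 |

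For a sustained value at baseline 60%, limb 2 brings the last ratio down to 70/25 = 2.8.

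**Sensitivity to the meaning of baseline.** If baseline were read as the lowest on-study value, limb 1 would need 3 + 15 = 18% after an MLFS at 3%. It would need 5 + 15 = 20% or 25 + 15 = 40% after a PR at 5% or 25%. The rule would be earlier but would still not mark loss of the response.

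**When limb 2 can be documented.** From cycle 3, scheduled response marrows are 3 x 28 = 84 days apart, at most 84 + 6 = 90 days with the ±3-day windows. Three months is about 365.25/4 = 91.3 days. Read strictly, two consecutive scheduled marrows fall just short, so limb 2 may need a third (6 x 28 = 168 days) or an unscheduled one. The calendar has a marrow at end of treatment but none at the 90-day visit, and section 6.4 then follows patients for survival.

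**The case against.** **PD does catch these patients eventually.** This stands in part: PD is a late rule, not an absent one. A reader might infer that blasts can go from 3% to 85% and simply be stable disease, or that marrow PD is impossible from a baseline above 66.7%. The documents do not support either. An 85% marrow escapes limb 1 only if baseline is at least 85/1.5 = 56.7%, and if it persists for 3 months without count improvement, limb 2 makes it PD. From above 66.7% limb 1 cannot be met, but limb 2 still can.

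**All responders are treated alike as written.** This also stands. A reader might infer that regrowth to 5% ends a CR or CRi while MLFS and PR run on, so that the weaker responses look more durable. Section 9.4.3 does not name relapse for anyone, so that contrast arises only if relapse is read as progression. On either reading MLFS and PR have no criterion.

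**The cited IWG criteria may contain a rule.** Sections 9.1.2.1, 9.6.2 and 11 cite AML IWG 2003 and MDS IWG 2006, but neither text is reproduced, and the 12.1 table credits a 2017 expert-panel AML recommendation. What those criteria say cannot be checked here, and with several sources named they cannot be relied on to fill the gap.

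**Investigators would record obvious regrowth as progression.** Section 9.4.3 does not tie progression to the PD row, and section 6.3 lists clinical progression separately from disease progression. Some losses may be recorded that way, but that is discretion, not a criterion.

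**Few PR patients may be followed on treatment.** Section 6.3 lists absence of CR/CRh/mCR as a reason to stop in patients without prior IDH inhibitor exposure, which may limit scheduled marrows after PR in those arms. Marrow CR (the name 12.1 also gives to MLFS) is on that list, so MLFS patients can remain on treatment with DOR running.

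**Conclusion.** The point holds: MLFS and PR start DOR, and 12.1 has no criterion for their loss. After an MLFS, marrow blasts can reach 5 to 14 times the level at which MLFS stops being met (baselines of 10% to 60%) without a sustained-marrow PD event. After a PR, the limb 1 threshold is about 3 to 3.6 times the PR limit (baselines of 20% to 60%). These figures assume that baseline means pretreatment and that the peripheral-blast and extramedullary limbs are not met.

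The bias in DOR is upward. Its size in months cannot be given, because the documents contain no regrowth rates or expected numbers of MLFS and PR.

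A reader might extend this to the main result. That is not supported: the primary endpoint is CR + CRi + CRh and the Simon boundaries use it alone. Nor does it follow that loss of PR should be a PFS event. At baseline 60%, a responder moving from 25% to 26% would then progress, while a never-responder steady at 60% would not. The change is worth making, but it concerns a secondary endpoint.

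**What to change.** For endpoint analysis only, leaving PD and the treatment-stopping rules as they are:

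1. **Section 12.1, relapse row:** extend it to CRh and MLFS. For MLFS, use marrow blasts of 5% or more, or new extramedullary disease. Do not use blood blasts, because the MLFS definition in 12.1 does not require their absence.
2. **Section 12.1, new row for loss of PR:** the PR marrow-blast criteria are no longer met on a scheduled marrow, meaning blasts above 25% or less than a 50% decrease from pretreatment.
3. **Section 9.4.3, DOR:** name relapse (after CR, CRi, CRh or MLFS) and loss of PR as events that end DOR. Changing 12.1 alone would not alter DOR, since 9.4.3 does not mention relapse. Do not add loss of PR to the PFS definition.

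The cost is two entries in 12.1 and one line in 9.4.3, using marrows already in the study calendar. The downside is a shorter DOR. Where a PR patient stops treatment early, the loss may still go undocumented after the end-of-treatment marrow.
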